#### Physical risks

Urea is a dietary supplement considered by the US Food and Drug administration under the GRAS (Generally Regarded As Safe) category. Urea is now available for the treatment of hyponatremia in the United States and evidence from case series in Europe and from a recent study by our group suggests that urea is safe and well-tolerated. Nevertheless, some patients might experience distaste, nausea, vomiting, diarrhea, and/or headaches associated with the use of urea. Osmotic demyelination syndrome is a complication of overly rapid correction of PNa (increase in PNa >8 mmol/L/24 hours) in patients with severe hyponatremia (PNa < 120 mmol/L). However, this is not a concern in our study population as patients with a PNa ≥125 mmol/L who do not have serious liver disease (an exclusion criterion for our study) have a negligible risk of osmotic demyelination syndrome if overcorrection of hyponatremia occurs.

#### Psychological risks

There are no anticipated psychological risks.

No social, cultural, financial or legal risks for the study participants are anticipated. Pregnant women are excluded from this study. However, no birth defect have been observed and currently there is inadequate information to conclude whether urea is mutagenic.

## 7.1.2 Risk of Study Procedures

- Blood draws: It may cause pain and bruise. Some people may become light-headed (dizzy) or faint after blood drawing. There is also a rare risk of infection at the site of the blood draw
- Fluid restriction: it may cause thirst.
- Neurocognition assessment: no known risks are associated with this study procedure.
- Posture stability assessment: There is a risk of falling while undertaking the balance testing, and this is heighted with increased age. All participants will use a safety harness during posture stability assessment.
- Collection and storing of PHI and Bio specimens: low risk of breach of confidentiality
- Discontinuing clinically prescribed urea in the hospital: This might cause the blood sodium level to decrease. To minimize this risk, we will first obtain approval from the participant's treating physician in the hospital to make sure is safe to do so and schedule participants for the screening visit within 5-7 days of hospital discharge to ensure a blood sodium level will be checked after urea discontinuation. In addition, we are only enrolling participants with a blood sodium level no lower of 125 mmol/L where the risk of experiencing any symptoms related to low blood sodium is very low.

## **6.2 ALTERNATIVE TREATMENTS**

Alternative treatments include fluid restriction alone, loop diuretics with salt tablets, and tolvaptan.

### **6.3 POTENTIAL BENEFITS**

There is no direct benefit to study participants. The results will provide proof of concept data and inform the design of a future randomized controlled trial which may profoundly impact the treatment of patients with chronic hyponatremia. However, the study interventions convey a very low risk in relationship to the therapeutic benefits for future patients with chronic hyponatremia. All patients will be offered the opportunity to be seen in the UPMC kidney clinic after completion of the study for consideration of continuation of urea therapy as part of their routine clinical care.

#### 7. RISKS MANAGEMENT PROCEDURES

### 7.1 PROTECTION AGAINST RISKS

#### General Risks of Study Protocol and Procedures

All research interventions/activities will be conducted in private patient care areas. The collection of sensitive information about subjects is limited to the amount necessary to achieve the aims of the research, so that no unneeded sensitive information is being collected. All demographic and clinical information about the subject will be stored in an electronic password-guarded study database under the supervision of the Investigator for this protocol.

The data will be stripped of individual identifiers and stored anonymously with a subject number. Information linking subject identifiers with the coded subject number will be stored under password protection on computers in locked areas, with access only to the database manager. All staff will sign confidentiality statements. Access to the database will be limited to the data manager and staff under the supervision of the Investigator.

All staff involved in this study are properly credentialed and instructed in the areas of testing, confidentiality, and safety.

The investigators will retain the data for the entire period of this study and will retain the specified records and reports for up to two years after the marketing application is approved for the investigational drug; or, if a marketing application is not submitted or approved for the investigational drug, until two years after investigations under the IND have been discontinued and the FDA so notified. The investigators may continue to use and disclose subjects' deidentified information for the purpose of this study for a minimum of seven years after final reporting or publication of the study. If the subject and/or legal representative decide to withdraw or be withdrawn from study participation, they may request that the study data be destroyed. Subject names or other directly identifiable information will not appear on any reports, publications, or other disclosures of clinical study outcomes.

Clinical study data that will be recorded directly on the electronic database include patient demographics, medications, comorbidities, and laboratory data whereupon the electronic data is to be considered Source Data. Source Data are the clinical findings and observations, laboratory and test data, and other information contained in Source Documents. Source documents may include, but are not limited to, hospital records, clinical and office charts,

laboratory notes, memoranda, subjects' diaries or evaluation, checklists, pharmacy dispensing records, recorded data from automated instruments, copies or transcriptions certified after verification as being accurate and complete, microfiches, photographic negatives, microfilm, or magnetic media, x-rays, subject files, and records kept at the pharmacy, at the laboratories, and at the medico-technical departments involved in the clinical trial. When applicable, information recorded on the CRF shall match the Source Data recorded on the Source Documents.

We will account for any missed, unused, and/or spurious data as follows: the extent and reasons that data are missing will be described. A comparison of baseline characteristics and intermediate outcomes between those who complete the study and those who do not will be conducted. We will investigate the randomness of missing data using available information on patient characteristics to help discern patterns in the missing data and to identify the possible covert missing data mechanisms. The primary efficacy analytic approach (mixed models) can handle data that are ignorable missing (i.e., either missing completely at random or missing at random). However, strategies to handle missing data (single/multiple imputation, selection models, pattern-mixture models, etc.) and sensitivity analyses to encompass different scenarios of assumptions will be considered as appropriate.

# 7.2 PROTECTION AGAINST POTENTIAL RISKS OF EXPERIMENTAL INTERVENTION

- Involvement of trained staff / investigators with experience in the administration of the study drug
- Continuous monitoring by the Data and Safety Monitoring Board
- Required Education in the Protection of Human Research Participants (CITI Good Clinical Practice Module)

## 8.0 ADVERSE EVENTS

The proposed study will use the FDA definition of adverse events (AE) and serious adverse events (SAE). Any SAE, which is unexpected and related to study intervention, will be reported immediately to the IRB and FDA and will include all known details regarding the nature of the SAE. In the event that a participant either withdraws from the study or the investigators decide to discontinue a participant due to a SAE, the participant will be monitored by the PI and treating investigator until (a) a resolution is reached (e.g., the problem has resolved or stabilized with no further change expected), (b) the SAE is determined to be clearly unrelated to the study intervention, or (c) the SAE results in death. Outcomes of SAEs not previously reported will be reported to the sponsor, IRB and FDA via a follow-up report. A summary of the SAEs that occurred during the previous year will be included in the FDA annual progress report as well as in the annual IRB renewal.

The severity of adverse changes in physical signs or symptoms will be classified as follows:

- Grade 1 (Mild): asymptomatic or mild symptoms; clinical or diagnostic observation only; intervention not indicated.
- Grade 2 (Moderate): minimal, local or noninvasive intervention indicated; limiting ageappropriate ADL (Activities of Daily Living).

- Grade 3 (Severe): medically significant but not immediately life-threatening; hospitalization or prolongation of hospitalization indicated; disabling; limiting selfcare/ADL.
- Grade 4 (Life-threatening): consequences; urgent intervention indicated.
- Grade 5 (Death): event is a direct cause of death.

### 8.1 REPORTABLE ADVERSE EVENTS

For this study, a serious adverse event is any untoward clinical event that is thought by either the investigator or the sponsor to be unexpected and at least possibly related to the study and results in any of the following:

- 1. Death
- 2. A life-threatening adverse event
- 3. Inpatient hospitalization or prolongation of an existing hospitalization
- 4. A persistent or significant incapacity or substantial disruption of the ability to conduct normal life functions
- 5. A congenital anomaly or birth defect
- 6. Important medical events that may not result in death, be life threatening, or require
- 7. Hospitalization may be considered serious when, based upon appropriate medical judgment, they may jeopardize the patient, or subject, and may require medical, or surgical intervention to prevent one of the serious outcomes listed above.

If clinically important and unexpected adverse experiences or clinically important study-related adverse experiences occur, they will be recorded on the adverse event case report form.

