## 8.2 ADVERSE EVENTS REPORTING TIMELINES

Life-threatening or fatal unexpected adverse events associated with the use of the study drug or procedures must be reported to the IRB within 24 hours of discovery of the incident with subsequent follow-up submission of a detailed written report.

The FDA will be notified by telephone or facsimile transmission of a human adverse event that is fatal or life-threatening no later than 7 calendar days after receiving the respective human adverse event information, followed by the subsequent submission of a written IND Safety Report.

Serious and unexpected adverse events associated with the use of the study drug or procedures will be reported to the IRB with subsequent follow-up submission of a detailed written report in accordance with the respective policies and procedures of the IRB. Written IND Safety Reports will be submitted to the FDA as soon as possible and, in no event, later than 15 calendar days following the investigator-sponsor's receipt of the respective adverse event information.

A summary report of the findings will be prepared and submitted to the regulatory agencies as required.

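### Section 8.1 makes unexpectedness and possible relatedness part of the SAE definition, in conflict with 8.0 and 8.2, so some serious events could be mislabelled and left out of the annual SAE summary

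*Combined protocol and SAP*

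**What the plan says.** **SAE definition.** Section 8.0 opens with a commitment: "The proposed study will use the FDA definition of adverse events (AE) and serious adverse events (SAE". It then says: "Any SAE, which is unexpected and related to study intervention, will be reported immediately to the IRB and FDA". For a participant who leaves the study because of an SAE, it lets monitoring end once the SAE is found clearly unrelated to the intervention. Two further outputs in 8.0 carry the SAE label. One is the yearly report: "A summary of the SAEs that occurred during the previous year will be included in the FDA annual progress report", with the same summary going into the IRB renewal. The other is follow-up: "Outcomes of SAEs not previously reported will be reported to the sponsor, IRB and FDA via a follow-up report".

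Section 8.1 then states that, for this study, an SAE is an untoward clinical "event that is thought by either the investigator or the sponsor to be unexpected and at least possibly related to the study", and that it must also result in one of the listed outcomes, such as death or hospitalization.

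Section 8.2 sets the timelines. "Serious and unexpected adverse events associated with the use of the study drug or procedures will be reported to the IRB", with a written FDA report within 15 calendar days. It also requires notice to the FDA of "a human adverse event that is fatal or life-threatening no later than 7 calendar days" after the information is received.

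**Form rule.** Section 8.1 ends: "If clinically important and unexpected adverse experiences or clinically important study-related adverse experiences occur, they will be recorded" on the adverse event case report form. Section 2.5.4 promises a report of everything adverse that occurs on urea, with seriousness, severity and possible relatedness for each event. Primary objectives o and p (section 1.1) and primary endpoints 16 and 17 (synopsis) concern urea-related adverse events and set no threshold of importance.

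**The concern.** Seriousness, expectedness and relatedness are three separate judgements. Section 8.1 folds all three into the word serious, whereas 8.0 and 8.2 keep them apart. A coordinator or investigator who follows 8.1 literally will give some events a different label from one who follows 8.0. Any output that selects on the SAE label then depends on which section was read. The output most clearly exposed is the annual SAE summary, which regulators and the IRB use to see serious events regardless of attribution.

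The form rule raises a smaller question of the same kind. The only stated rule on what must go on the adverse event form is narrower than the safety report and the primary endpoints for which that form would be the natural source.

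**Working it through.** This is a check of the text. The FDA definition is not reproduced in the documents, so nothing below relies on its content. The comparison assumes that the outcomes listed in 8.1 would count as serious under either section.

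**Step 1: how 8.0 and 8.2 use the two tests.** Section 8.0 names unexpected and related when it says which SAEs go out immediately. It also foresees an SAE that turns out to be unrelated. Section 8.2 asks for events that are serious and unexpected and associated with the drug or procedures. If every SAE were already unexpected and possibly related, these added conditions would do no work, and an unrelated SAE would be close to a contradiction.

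**Step 2: one event, four classifications.** Take a hospitalization that is not immediately life-threatening.

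| Judged | SAE under 8.0 | SAE under 8.1 | Immediate report under 8.0 | In annual summary if 8.0 governs | In annual summary if 8.1 governs |
|---|---|---|---|---|---|
| Unexpected, related | yes | yes | yes | yes | yes |
| Unexpected, unrelated | yes | no | no | yes | no |
| Expected, related | yes | no | no | yes | no |
| Expected, unrelated | yes | no | no | yes | no |

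The label differs in three of the four rows. In those three rows 8.0 requires no immediate report under either definition, so the conflict leaves immediate reporting essentially unchanged. The 7-day FDA notice for fatal or life-threatening events in 8.2 does not use the SAE label at all. What changes is the annual summary.

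**Step 3: the follow-up reports.** These also select on the SAE label. However, the sentence directly follows one about participants who withdraw or are discontinued because of an SAE, and a follow-up report may presuppose an initial one. This output is possibly exposed, not certainly.

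**Step 4: the form rule.** Both branches of the 8.1 rule require clinical importance, which is not defined. The rule does not exclude other events, but it does not require them. Section 2.5.4 and endpoints 16 and 17 have no such threshold. Other routes could capture the remainder:
- questions on new symptoms at days 7, 14 and 42 of each period, and side-effect questionnaires (section 2.2);
- a CRF category for adverse experiences (section 2.5.6);
- staff reports of all adverse events to an investigator (section 9.2).

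The documents do not name which of these is the source for the 2.5.4 report or the two endpoints.

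**Step 5: the only related figure.** Section 2.5.1 gives margins of error of 8% and 11% for adverse event rates of 5% and 10% with 30 patients. They reproduce:
- 1.96 × √(0.05 × 0.95 / 30) = 7.8 points;
- 1.96 × √(0.10 × 0.90 / 30) = 10.7 points.

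These margins describe sampling error only. They say nothing about how many events would be mislabelled or left off the form.

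**The case against.** The best defence is that 8.1 is headed as a section on reportable events. Its author probably meant a reporting filter, and 8.0, with the FDA definition, governs. The intent is plausible, but the sentence is worded as a definition for this study and gives staff a second rule. One could also read the comma clause in 8.0 on immediate reporting as describing every SAE, which would bring 8.0 into line with 8.1. That reading sits badly with 8.0's own allowance for an SAE that proves unrelated, and it leaves 8.2 with redundant conditions.

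A reader might infer that serious events would go unreported. The documents do not support that. Section 9.2 has staff pass all adverse and serious adverse events to an investigator at once. The investigator reports them to the IRB as institutional requirements dictate, and they should also be communicated to the IND sponsor. No test of expectedness or relatedness applies there.

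A reader might also infer that mild urea-related events will be missed and that the endpoint 16 proportion will be biased low. That would follow only if the adverse event form were the sole source, which no section says. Mild is also not the same as clinically unimportant: the listed gastrointestinal symptoms and headache can lead to dose reduction or discontinuation if they persist (section 10), so persistent ones could well qualify. The side-effects questionnaire and the manual of procedures are not in the text provided and may close the gap. This part of the objection largely stands, and it reduces the form rule to a minor alignment point.

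**Conclusion.** The SAE definition in 8.1 conflicts with 8.0 and 8.2 and should be corrected; confidence is high. If 8.1 is applied as written, serious events judged expected or unrelated lose the SAE label and could be left out of the annual FDA and IRB summary, and possibly out of the follow-up reports of SAE outcomes. The consequence is misclassification in summaries. The events themselves should still reach an investigator, and urgent reporting is largely intact. The number of events affected cannot be derived.

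The form rule is narrower than section 2.5.4 and primary endpoints 16 and 17; confidence that this matters is moderate. It is a missing link in the data flow, not a shown loss of data, and no size of under-recording can be calculated from the documents.

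**What to change.** 1. In 8.1, remove the unexpectedness and relatedness conditions from the SAE definition, or relabel that sentence as the subset of SAEs for expedited reporting. The 8.0 definition then governs throughout, and the two tests act only as reporting filters.
2. As a minor companion change, reword the 8.1 form rule so that every adverse event is recorded on the adverse event form, with seriousness, severity grade, expectedness and relatedness as separate fields. State that this form is the source for the 2.5.4 report and for primary endpoints 16 and 17.

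The cost is a wording change in 8.1 and, if they are not already there, extra fields on one form. No visit or test is added. The downside is more low-grade events to record.

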## 8.2 ADVERSE EVENTS REPORTING TIMELINES

Life-threatening or fatal unexpected adverse events associated with the use of the study drug or procedures must be reported to the IRB within 24 hours of discovery of the incident with subsequent follow-up submission of a detailed written report.

The FDA will be notified by telephone or facsimile transmission of a human adverse event that is fatal or life-threatening no later than 7 calendar days after receiving the respective human adverse event information, followed by the subsequent submission of a written IND Safety Report.

Serious and unexpected adverse events associated with the use of the study drug or procedures will be reported to the IRB with subsequent follow-up submission of a detailed written report in accordance with the respective policies and procedures of the IRB. Written IND Safety Reports will be submitted to the FDA as soon as possible and, in no event, later than 15 calendar days following the investigator-sponsor's receipt of the respective adverse event information.

A summary report of the findings will be prepared and submitted to the regulatory agencies as required.

#### 9. DATA SAFETY MONITORING

# 9.1 DATA SAFETY MONITORING BOARD

A Data Safety Monitoring Board (DSMB) will be appointed for this study. The DSMB will be composed of 3 members to be named.

# 9.2 DATA SAFETY MONITORING PLAN

Monitoring of safety and data quality in the proposed study will be the responsibility of all personnel on the project, with primary responsibility and supervision by the Investigator. The Institutional Review Board will approve the Statement of Informed Consent for the study and provide institutional oversight of data and safety issues. The study protocol will be approved prior to recruiting or obtaining consent from any participants. Moreover, the study will be reviewed at a minimum of annual basis (or more frequently as deemed necessary) by the IRB committee. Each participant will sign the Informed Consent Form described above prior to participating in the study. To ensure participant safety, once participants are enrolled in the study, study staff will immediately report all adverse and serious adverse events to one of the Investigators. The Investigator will, per institutional requirements, report them to the IRB for their review. These events should also be communicated to the sponsor of the IND. With regard to monitoring of data guality and protected health information, all required personnel proposed for this project will have the required human subjects and confidentiality training, which includes information about maintaining data integrity and security. Confidentiality will be guarded using established procedures such as storing data in locked cabinets within locked offices or locked data rooms, coding by study identification numbers rather than any personally identifying information to avoid revealing the identity of subjects, and aggregating data across participants. The key linking names and study identification numbers will be kept separately from the data sets with limited access by study personnel. Only study personnel will have access to the data sets on protected servers. In order to maintain the highest standard of data entry quality, all data will be double-entered, with discrepancies highlighted so that they can be reviewed by the project coordinator. Oversight of all aspects of data management will occur with the Investigator.

